11.1 Determination of sample size

The sample size estimation for this study is based on the primary efficacy endpoint, time to the absence of need for oxygen supplementation. When use a two-side alpha value of 0.05 and assume the proportions of patients who do not need oxygen supplementation by day 14 are 83% and 40% for mavrilimumab and placebo arms respectively, total 28 events are required to achieve a 90% power using a log-rank test.

Approximately total 50 patients will be randomized with a 1:1 ratio to obtain the total target number of events. Analysis for treatment effect will be based on the evaluable population which includes all subjects who are randomized and receive KPL-301/placebo treatment.

11.2 Statistical analysis

All efficacy analysis will be done based on the evaluable population.

The primary efficacy endpoint, time to the absence of need for oxygen supplementation will be assessed after all patients have reached day 14, with failure to reach absence of need for oxygen supplementation or death before day 14 considered as right-censored at day 14. Logrank test stratified by randomization stratum respiratory insufficiency status (mild vs moderate) will be done to compare the efficacy between the two treatment arms. Hazard ratio and its 95% CI will be estimated using the Cox proportional hazards model. Kaplan–Meier curves will also be provided for each treatment arm.

Subgroup analysis for the primary efficacy endpoint will be done to evaluate the robustness of the data base on the following baseline characteristics using the same methodology as specified above:

- Age ($<50 \text{ vs. } 50-69 \text{ vs. } \ge 70$)
- Respiratory insufficiency status (mild vs. moderate)

For other time to event endpoints, the same methodology used for the primary efficacy endpoints will be repeated. For binary endpoints, Cochran–Mantel–Haenszel test adjusted by the respiratory insufficiency status will be conducted. For continuous endpoints, ANCOVA will be done with treatment as the independent variable and baseline, baseline by treatment interaction, and baseline respiratory insufficiency status as the covariate.

Other than respiratory insufficiency status, no other randomization strata will be used in the stratified analysis due to the small sample size of this study. For any stratified analyses, if one stratum has ≤ 5 events of interest in a log-rank test or the same response in all patients in a CMH test, the analysis will be done without stratification.

Incidence rate of treatment emergent adverse events will be summarized. Descriptive statistics will be done for other safety assessments.

12. Ethical and legal aspects

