3.2 Secondary objectives and secondary endpoints

Secondary objective	Secondary endpoints
To evaluate clinical outcomes using the 7-point ordinal scale (APPENDIX 1) in patients with COVID-19	- Proportion of responders at day 7, 14, and 28 based on the 7-point ordinal scale. Response is defined as a 7-point ordinal scale of 3 or less, i.e. no supplemental oxygen
	 Time to response, defined as time from date of randomization to the date with a 7-point ordinal scale of 3 or less, i.e. no supplemental oxygen
	- Proportion of patients with at least two-level improvement in clinical status at day 7, 14, and 28
	- Baseline change of clinical status to day 7, 14, and 28
To evaluate the time to disappearance of fever if present at baseline	Time to resolution of fever (for at least 48 hours) in absence of antipyretics, or discharge, whichever is sooner in the 4-week period after

IRCCS San Raffaele Scientific Institute Protocol (v 3.1 – 01 mag 2020)

	study treatment. Resolution of fever is defined as body temperature:
	- ≤36.6°C (axilla) or
	- ≤37.2 °C (oral), or
	- ≤37.8 °C (rectal or tympanic)
	Note: Fever is defined as defined as body temperature > 37.4°C [axilla], or > 38.0 °C [oral], or >38.4°C [rectal or tympanic].
To demonstrate the potential benefit of mavrilimumab in reducing the case fatality rate over 4 weeks among patients with COVID-19 pneumonia and hyperinflammation regardless of other subsequent clinical interventions	COVID-19-related death during the 4-week period after study treatment (in hospital and overall)
To evaluate the in-hospital outcomes in patients with COVID-19 pneumonia and hyperinflammation	Proportion of hospitalized patients who died or required mechanical ventilations (WHO Categories 6 or 7) by day 14
To evaluate change in laboratory parameters through follow up	Variations of the following serological markers over follow-up:
	- C-reactive protein
	- Ferritin
	- D-Dimer
To evaluate changes in the National Early Warning Score 2 (NEWS2, Appendix 2)	- Median changes of NEWS2 score from baseline at day 7, 14, 28 (or discharge, whichever comes first)
	- Time to clinical improvement (as defined as a NEWS2 score of 2 or less maintained for at least 24 hours or discharge, whichever comes first)

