8.1 Schedule of Assessment and Procedures (table 1)

	(0-24 hrs prior to dose)	(investigational drug dosing)	п	hospitalization until day 28 or discharge (whicever is earlier)	7*	14*	28 (or at discharge)*	*34 -/+	(+- 7 days) End of study*
		S	T U D	YPEF	R I O	D		FOLLOW	U P
informed consent	×								
Inclusion/exclusion criteria	×	x(2)							
Demographics / medical history /relevant comorbidities	×								
SarsCoV-2	x(1)	REC	CORD ALL SA	RECORD ALL SARS-COV-2 DETERMINATIONS AS OBTAINED	S AS OBTAIN	ED	×	x (if available)	x (if available)
Vital signs (HR, RR, SpO2 and/or PaO2, BP, body temp)	×	x(2)	×	×	×	х	×		
Oxygen delivery (flow + FiO2)	×	x(2)	×	×	×	×	×	×	×
NIV use (hours/day)	×	x(2)	×	×	×	×	×		
Height, weight	×								
Physical		5(2)	S						
Clinical status with the 7-point ordinal scale		x(2)	×	×	×	×	×	×	×
Vital status (and if applicable, cause of death)			×	×	×	×	×	×	×
Blood cultures (Aer/Anaer)		x(3)							
Hematology (Hb, MCV, WBC, Plt, absolute count of N,L,M,E,B)	×		×	x every other day until discharge	×	×	×	x (if available)	x (if available)
Clinical chemistry (AST, ALT, ALP,									
LDH, creatine kinase, troponin,	>		>	x every other day until	,	>	,	v (if everience)	(aldelieve fi) v
chicoco total protoin CBD forritin	<		<	discharge	<	<	<	v (II available)	A (II available)
glucose, total protein, chr., refritiil, D-dimer; IL-6 [if available])									
Pregnancy test (if applicable)	S								
CT scan / chest X-ray	x(1)		RECORD ALL	RECORD ALL PULMONARY IMAGING AS OBTAINED	OBTAINED		x (if available)		
Electrocardiogram	S(1)								
Adverse events	×	x(2)	×	×	×	×	×	×	×
Prior / concomitant medications	×	x(2)	×	×	×	X	×	×	×
Randomization		x(2)							
Study drug administration		x(2)							
In-hospital outcomes:									
Days on non-invasive ventilation		x(2)	×	 	 	 	×		
Days on mechanical ventilation		x(2)	 	 		 	×		
Days in hospital		x(2)	×	×		×	×		
Days in ICU		x(2)	×	×		×	×		
Days with use of supplemental O2		x(2)	×	×		×	×		
Days on ECMO		x(2)	×	×		×	×		
Blood collection for experimental		x(2)		x (day 5)	x (if	x (if	x (if possible)	x (if possible)	x (if possible)

x to be recorded into the eCRF

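### The time-to-event and binary analyses adjust only for mild vs moderate PaO2/FiO2 and leave recorded baseline respiratory support (score 4 vs 5) unused

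*Protocol*

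**What the plan says.** Protocol section 11.2 fixes the primary comparison: "Logrank test stratified by randomization stratum respiratory insufficiency status (mild vs moderate) will be done to compare the efficacy". For the effect estimate it says "Hazard ratio and its 95% CI will be estimated using the Cox proportional hazards model", with no strata and no covariates named. Other time-to-event endpoints repeat this method. Binary endpoints get a Cochran–Mantel–Haenszel (CMH) test adjusted for the same two-level factor. Continuous endpoints are handled differently: their ANCOVA includes the baseline value as well as respiratory status.

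The section rules out further randomization strata because the study is small. It also drops stratification altogether if a stratum has five or fewer events.

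Table 1 in section 8.1 schedules "Clinical status with the 7-point ordinal scale" on the dosing day, with a footnote that assessments that day precede dosing. Oxygen flow with FiO2, hours of non-invasive ventilation, and SpO2 and/or PaO2 are recorded at screening and before dosing. Section 3.2 lists among the secondary endpoints: "Proportion of patients with at least two-level improvement in clinical status at day 7, 14, and 28".

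**The concern.** Every enrolled patient needs oxygen, and section 5.2 excludes mechanical ventilation but neither non-invasive ventilation nor high-flow oxygen. Baseline scores are therefore 4 (simple oxygen) or 5 (non-invasive ventilation or high flow). The primary event is coming off oxygen, and a patient at 5 plausibly starts further from it. Two patients in the same PaO2/FiO2 stratum can differ in this respect, and the planned time-to-event and binary analyses do not separate them.

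The two-level improvement endpoint has a sharper problem that follows from the scale itself. A patient at 5 responds by reaching 3, still in hospital but off oxygen. A patient at 4 must reach 2, which means having left hospital. Baseline score thus defines the hurdle, yet the test ignores it.

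At stake is the credibility of the hazard ratio and responder differences in a trial of about 50. If the arms happen to differ in support level, readers will ask how much of the result reflects that, and a covariate chosen after unblinding would not be a convincing answer.

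**Working it through.** **Plan's own figure.** Section 11.1 gives "When use a two-side alpha value of 0.05", day-14 proportions of 83% and 40%, and "total 28 events are required to achieve a 90% power using a log-rank test".
- Implied hazard ratio = ln(1 − 0.83)/ln(1 − 0.40) = 3.47.
- Schoenfeld events = 4 × (1.960 + 1.282)² / (ln 3.47)² = 42.03/1.547 = 27.2, so 28. The stated figure reproduces.
- Expected events in 50 patients = 25 × 0.83 + 25 × 0.40 = 30.75, about 31.

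**How often support is imbalanced.** The documents do not give the share at score 5; 40% is assumed.
- Two independent Binomial(25, 0.4) arms: P(difference ≥ 6 patients, e.g. 7 vs 13) = 11.1%.
- Exactly 20 of 50 at score 5, split at random: 14.8% (the difference can then only be even).
- If support tracks the randomization stratum, balance within strata lowers this. With half the patients moderate and score 5 in 25%/55% of mild/moderate patients it is about 9 to 10%; with 20%/60%, about 8%; with 10%/70%, about 4 to 5%.

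**What it does to the hazard ratio.** Assume score 5 has hazard h relative to score 4, with h between 0.4 and 0.6 (not in the documents). Approximate shift factor = exp[(6/25) × ln h].
- h = 0.4: exp(0.24 × −0.916) = 0.80; inverse 1.25.
- h = 0.6: exp(0.24 × −0.511) = 0.88; inverse 1.13.

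The event is favourable, so an excess of score 5 in the mavrilimumab arm pulls the ratio down and an excess in the placebo arm pushes it up.

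**Check by simulation.** 1,500 trials per scenario; 50 patients; allocation balanced within mild/moderate; score 5 in 25% of mild and 50% of moderate; moderate vs mild rate ratio 0.6; true hazard ratio 3.47; Cox model stratified by respiratory status.

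| Score-5 rate ratio | Hazard ratio multiplied by, for a 20-point excess in active arm | Median hazard ratio, stratified only | Median, score added |
|---|---|---|---|
| 0.6 | 0.93 | 3.41 | 3.57 |
| 0.4 | 0.82 | 3.19 | 3.55 |
| 0.25 | 0.78 | 2.91 | 3.54 |

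With score in the model, the shift per 10 points of imbalance was at most 0.02 on the log scale. With no treatment effect, both analyses rejected in about 5 to 6% of trials.

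**Two-level improvement endpoint.** Simulated CMH tests stratified by baseline score rather than by PaO2/FiO2 gave from nil to about 11 points more power, with type I error held near 5%. The gain is nil when response rates do not differ by baseline score and grows as they diverge.

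**The case against.** The strongest defence is that nothing here is invalid. A log-rank test stratified by a randomization factor is standard, and a reason is given for using no more strata. Chance imbalance is random error that the confidence interval already covers. With 30.75 expected events, SE(log HR) ≈ 2/√30.75 = 0.36, so the 95% interval spans a factor of exp(1.96 × 0.36) ≈ 2.0 each way. A shift of 0.80 (0.22 on the log scale) is about 0.6 of a standard error. Sensitivity models may also be in an SAP that is not shown. All of this stands and keeps the point small. It does not answer why the named primary estimate omits a prognostic baseline value already collected. The small-sample reason covers extra randomization strata, not one or two regression covariates.

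A reader might infer three stronger claims that the documents do not support:
- **That all analyses ignore baseline.** The ANCOVA for continuous endpoints includes it; for the PaO2/FiO2 endpoint that is the measured ratio.
- **That imbalance feeds fully into the hazard ratio as bias.** Randomization and the log-rank test are stratified on PaO2/FiO2, which absorbs the part that follows the stratum. The remainder averages to zero over trials.
- **That the primary test would gain power.** In the simulation, power went from 0.91, 0.87 and 0.79 to 0.90, 0.90 and 0.87 for score-5 rate ratios of 0.6, 0.4 and 0.25. That belongs to a score-adjusted test, which is not proposed here.

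**Conclusion.** The point holds in limited form, as a worthwhile improvement rather than an error. It applies to the time-to-event and binary endpoints only. The size rests on an assumed 40% at score 5 and an assumed relative hazard of 0.4 to 0.6. If support is only weakly prognostic, little is lost. The baseline-dependent target in the two-level improvement endpoint needs no such assumption, because it follows from the scale.

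Two features of section 11.2 add to the case. The Cox model is not stated to be stratified even by respiratory status, so the hazard ratio need not correspond to the test reported beside it. The five-event rule can also remove the only adjustment the log-rank test has.

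**What to change.** In section 11.2 or the SAP, before unblinding:
- State that the Cox model is stratified by respiratory status.
- Prespecify baseline score (4 vs 5), and optionally continuous PaO2/FiO2, as covariates for the hazard ratio estimate.
- Keep the stratified log-rank as the primary test.
- Adjust the ordinal-scale responder endpoints for baseline score, for example by using it as the CMH stratum. Crossing it with mild/moderate would leave four cells averaging 50/4 = 12.5 patients.
- Report the estimate without score beside the adjusted one.

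No new data are needed. The cost is one or two extra parameters with about 31 expected events. The adjusted hazard ratio is also a conditional quantity that can differ somewhat from the one matching the log-rank test, which is why both should be shown.

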	 Any serious medical condition or abnormality of clinical laboratory tests that, in the investigator's judgment, precludes the patient's safe participation in and completion of the study In the opinion of the investigator, progression to death is imminent and highly likely within the next 24 hours, irrespective of the provision of treatments Current participation in any other interventional investigational trials
Study treatment	 Arm 1: Mavrilimumab 6 mg/kg IV infused over approximately 1 hour Arm 2: Matching placebo infused over approximately 1 hour Mavrilimumab or placebo infusions will be prepared and blinded by an unblinded pharmacist or designated staff member. Patients will be randomized according to their age (<50; 50-69; ≥ 70 yo), and their respiratory stratum (PaO₂/FiO₂ 200-300 or 100-199 mmHg) at randomization.
Treatment of interest	Randomized mavrilimumab or placebo as described above. In addition, all patients will receive standard of care per local practice for the treatment of COVID-19-induced pneumonia. The SOC may include but not be limited to anti-viral treatment, low-dose corticosteroids (≤ 15 mg of prednisone or equivalent) and/or hydroxychloroquine or chloroquine and/or supportive care.
Rescue treatment	In worsening patients, treatment with investigational COVID-19 treatments, such as but not limited to antimicrobials, interferon beta, or convalescent serum, is permitted, if approved by the Promoter. Particular attention should be taken when considering rescue treatment with biologic or targeted-synthetic DMARDs/immuno-suppressors due to the risk of potential severe immune-suppression if given in combination with the investigational drug. Systemic corticosteroids (low- or high-dose per medical judgement) could also be used as a rescue medication.
Efficacy assessments	The WHO-adopted 7-point ordinal scale of clinical status will be assessed on a daily basis at baseline and after study treatment during hospitalization as well as at day 7, 14, and 28. NEWS2 score will be assessed on a daily basis at baseline and after study treatment during hospitalization day 7, 14, and 28.

Safety assessments	Adverse event monitoring, physical examinations, and monitoring
	of laboratory safety values.
Other assessments	Standard safety and laboratory assessment (hematology and
	clinical chemistry) will be performed during hospital stay and
	outpatient visits after discharge from hospital (See Schedule of

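### The ANCOVA for continuous endpoints includes a baseline-by-treatment interaction but neither centres baseline nor says where the treatment effect is evaluated

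*Protocol*

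**What the plan says.** Section 11.2 sorts the non-primary endpoints into time-to-event, binary and continuous. For the continuous ones it specifies an ANCOVA that has, besides treatment, "baseline, baseline by treatment interaction, and baseline respiratory insufficiency status as the covariate". The interaction is part of the main model and is not called exploratory, supportive or conditional on a test. The section does not mention centring, adjusted means, or a baseline value at which the arms are compared.

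Section 3.2 lists the endpoints that fall to this model: change in clinical status on the 7-point scale, change in NEWS2, CRP, ferritin, D-dimer, and the course of PaO2/FiO2. The protocol has no separate method for ordinal change scores, so by elimination they go to the ANCOVA.

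Possible baseline values are partly fixed by design. The synopsis defines the "respiratory stratum (PaO₂/FiO₂ 200-300 or 100-199 mmHg) at randomization", and sections 5.1 and 5.2 admit only patients from 100 to 300 mmHg. Entry requires hospitalisation on oxygen and excludes mechanical ventilation, so the 7-point scale in section 8.4 can only be 4 or 5 at baseline.

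**The concern.** When treatment, baseline and their product are all in a linear model, the treatment effect depends on baseline. The coefficient labelled treatment is then the effect at one particular baseline value, zero, unless baseline has been shifted. For PaO2/FiO2 and the 7-point scale, zero lies well outside anything a trial patient can have. The term is therefore an extrapolation, whereas the objectives in section 3 ask about benefit in the enrolled population.

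Two things are at stake. The test of that term answers a question nobody asked, and it does so with a much larger standard error, so a real average effect could pass unnoticed. In addition, the stated model gives two very different p-values depending on how baseline is coded, and the protocol does not fix which one counts.

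**Working it through.** **The plan's own figure.** The only sample-size calculation is for the primary endpoint (section 11.1): "83% and 40% for mavrilimumab and placebo arms respectively", a "two-side alpha value of 0.05", and "total 28 events are required to achieve a 90% power using a log-rank test".

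- Hazard ratio = ln(1 − 0.83) / ln(1 − 0.40) = 3.47.
- Schoenfeld events = 4 × (1.960 + 1.282)² / (ln 3.47)² = 27.2, rounded up to 28.

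The figure reproduces. It does not involve the ANCOVA, and the protocol gives no target effect for any continuous endpoint.

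**The model.** Let T be treatment, X baseline and S respiratory stratum:

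y = a + bT + cX + dTX + eS + error.

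The arm difference at baseline x is b + dx. With 1:1 allocation, baseline similarly distributed in both arms, and baseline mean m and SD s, its variance relative to the model without interaction is about

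1 + (x − m)² / s².

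- At x = 0 (the coefficient b): factor 1 + m²/s².
- At x = m (baseline centred): factor 1.

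**Bounds from the protocol's ranges.** For any baseline confined to [p, q], the smallest possible value of 1 + m²/s² is 1 + 4pq/(q − p)².

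- PaO2/FiO2, 100 to 300: 1 + 4 × 100 × 300 / 200² = 4, so the SE is at least 2 times larger.
- 7-point scale, 4 to 5: 1 + 4 × 4 × 5 / 1² = 81, so the SE is at least 9 times larger.

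**PaO2/FiO2 assumed uniform on 100 to 300.** m = 200 and s² = 200²/12 = 3,333. The factor is 1 + 40,000/3,333 = 13, and the SE ratio is √13 = 3.61. Simulation gave 3.65.

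**Power with 50 patients, assumed effect 0.8 SD.**

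- Without interaction: SE = √(4/50) = 0.283 SD; 0.8/0.283 = 2.83; approximate power Φ(2.83 − 1.96) = 81%.
- Uncentred term: SE = 3.61 × 0.283 = 1.02; 0.8/1.02 = 0.78; approximate power Φ(0.78 − 1.96) = 12%.
- Simulation with t tests and the stratum in the model: about 78% and 11%. With baseline centred, power is again 78%.

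**Other endpoints.** Simulated with 50 patients, no true interaction and an effect of 0.95 SD, chosen so that power without the interaction is about 90%. All baseline distributions are assumptions; only the PaO2/FiO2 range and the values 4 and 5 come from the protocol.

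| Baseline | SE ratio, uncentred | Power without interaction | Power, uncentred | SE ratio, centred |
|---|---|---|---|---|
| 7-point scale, 4 or 5 evenly | 9.1 | 89% | 6% | 1.00 |
| PaO2/FiO2, uniform 100–300 | 3.65 | 89% | 15% | 1.00 |
| NEWS2, mean 6, SD 2 | 3.3 | 89% | 17% | 1.00 |
| CRP, mean 120, SD 60 | 2.3 | 90% | 28% | 1.00 |
| Ferritin, log-normal, sigma 0.8 | 1.6 | 90% | 52% | 1.00 |
| D-dimer, log-normal, sigma 1.1 | 1.34 | 90% | 68% | 1.00 |

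Power with baseline centred was 89% to 90% in every row.

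**The case against.** The strongest reply is that section 11.2 lists model terms only. It nowhere says that the raw treatment coefficient will be reported or tested. An ANCOVA with a separate slope in each arm is a legitimate model, and the difference between arms at the mean baseline comes from the same fit with essentially no loss. On this view the evaluation point is a detail that a statistical analysis plan, not shown here, would normally settle.

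Much of this stands. A reader might infer that the interaction itself costs precision, and the calculation shows that it does not: the loss belongs to the uncentred treatment term. A reader might also infer that the trial will report that term, which the protocol does not say. The power figures are therefore consequences of one literal reading, not predictions.

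The reply does not dispose of the point. The protocol has not left the model to a later document: it fixes an interaction in its only model for these endpoints. The treatment test of that model, as written, concerns a baseline that two of the endpoints cannot take. Section 11.2 also limits stratification because the trial is small, which sits badly with adding an interaction and leaving the main effect undefined.

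**Conclusion.** The point holds as a defect of specification in the non-primary analyses. Taken literally, the treatment term is the arm difference at baseline 0, with an SE at least about 2 times (PaO2/FiO2) and 9 times (7-point scale) that of the model without interaction. Those two bounds need only the entry ranges and comparable baselines in the arms; the second also takes change on the ordinal scale to be analysed as continuous. The factor of 3.6 and the fall in power from about 78% to 11% also assume a uniform baseline and, for power, a 0.8 SD effect.

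Two broader conclusions are not supported. One is that every continuous endpoint would lose most of its precision: under the assumed skewed baselines the SE ratio is about 1.6 for ferritin and 1.34 for D-dimer, so the loss in power is smaller there. The other is that the trial's main result is at risk: the primary endpoint uses a stratified log-rank test and a Cox model without this term, and the 28-event calculation is untouched.

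**What to change.** Amend the ANCOVA sentence in section 11.2 in one of two ways:

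- Make treatment, baseline and respiratory stratum the main model, and move the baseline-by-treatment interaction to a supportive analysis.
- Keep the interaction, centre baseline at the overall mean, and report the adjusted mean difference at that mean with its 95% CI as the treatment effect.

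In the simulations above, either choice gives practically the same precision for the average effect. The cost is one sentence, with no extra patients or data. It should be settled before unblinding, so that the coding of baseline is not chosen with the results in view.
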